4.4 Justification for Inclusion/Exclusion of Special Populations

Pregnant women: Pregnant women are excluded from this study because pregnancy may cause changes in the immune system that could confound study results. During the course of the study, if a subject becomes pregnant or suspects she is pregnant, she should inform the study staff and her primary care physician immediately. Pregnancies occurring during study participation will be managed as outlined in section 12.3.

Children: Children are excluded from this study because there is no possibility of benefit to subjects from the research being conducted. The seasonal influenza vaccine is available as part of standard preventive care outside of this study.

NIH staff: NIH staff may be enrolled in this study if they meet the study entry criteria. Neither participation nor refusal to participate in the research will have an effect, either beneficial or adverse, on an individual's employment or position at NIH.

Every effort will be made to protect subject information, but such information may be available in medical records and may be available to authorized users outside of the study team in both an identifiable and unidentifiable manner.

The NIH Information Sheet on Employee Research Participation will be made available. Please see section 16.2 for consent of staff members.

5 Study Vaccine

An investigational new drug application will not be submitted for the study vaccines being used in this protocol because the following exemption criteria are being met:

- The drug product is lawfully marketed in the United States.
- The investigation is not intended to be reported to the FDA as a well-controlled study in support of a new indication and there is no intent to use it to support any other significant change in the labeling of the drug.
- In the case of a prescription drug, the investigation is not intended to support a significant change in the advertising for the drug.
- The investigation does not involve a route of administration, dose, patient population, or other factor that significantly increases the risk (or decreases the acceptability of the risk) associated with the use of the drug product.
- The investigation is conducted in compliance with the requirements for review by an IRB and with the requirements for informed consent.
- The investigation is not intended to promote or commercialize the drug product.

5.1 Disposition, Dispensation, and Accountability

The study vaccine will be distributed and accounted for by the NIH pharmacy according to standard pharmacy procedures. Subjects will only receive one flu vaccine per year, which will be the vaccine provided by the NIH pharmacy.

5.1.1 Formulation and packaging

The study vaccine is a sterile suspension for intramuscular injection available in 0.5-mL prefilled syringes or a 5.0-mL multi-dose vial containing 10 doses of 0.5 mL each.

5.2 Study Agent Storage and Stability

The study vaccine should be stored in refrigeration at 2°C to 8°C (36°F to 46°F) and protected from light. It should not be frozen. The vaccine will not be used if it has been frozen or is past the expiration date. If the multi-dose vial is used, the vial will be returned to recommended storage conditions between uses.

5.3 Preparation, Administration, and Dosage of Study Agent/Intervention

5.3.1 Description

The specific study vaccine will be the vaccine stocked by the NIH pharmacy, either Flucelvax Quadrivalent or Fluvirin for subjects under 65 years (only one vaccine will be used during a given influenza season), or Fluzone High-Dose for subjects aged 65 years and older.

Flucelvax Quadrivalent: Flucelvax Quadrivalent is a subunit influenza vaccine prepared from virus propagated in Madin Darby Canine Kidney (MDCK) cells, a continuous cell line.¹² These cells were adapted to grow freely in suspension in culture medium. The virus is inactivated with β -propiolactone, disrupted by the detergent cetyltrimethylammonium bromide and purified through several process steps. Each of the 4 virus strains is produced and purified separately, and then pooled to formulate the quadrivalent vaccine.

Flucelvax Quadrivalent is a sterile, slightly opalescent suspension in phosphate buffered saline. It is standardized according to United States Public Health Service (USPHS) requirements for the current influenza season and is formulated to contain a total of 60 mcg hemagglutinin (HA) per 0.5-mL dose in the recommended ratio of 15 mcg HA of each of the four selected influenza strains. Each dose of Flucelvax Quadrivalent may contain residual amounts of MDCK cell protein (≤ 8.4 mcg), protein other than HA (≤ 160 mcg), MDCK cell DNA (≤ 10 ng), polysorbate 80 (≤ 1500 mcg), cetyltrimethylammonium bromide (≤ 18 mcg), and β -propiolactone (< 0.5 mcg), which are used in the manufacturing process.

Flucelvax Quadrivalent 0.5-mL pre-filled syringes contain no preservatives or antibiotics. Flucelvax Quadrivalent 5-mL multi-dose vial formulation contains thimerosal, a mercury

derivative, added as a preservative. Each 0.5-mL dose from the multi-dose vial contains 25 mcg mercury. Flucelvax Quadrivalent 5-mL multi-dose vial formulation contains no antibiotics.

Fluvirin: Fluvirin is a trivalent, sub-unit (purified surface antigen) influenza virus vaccine prepared from virus propagated in the allantoic cavity of embryonated hens' eggs inoculated with a specific type of influenza virus suspension containing neomycin and polymyxin.¹³ Each of the influenza virus strains is harvested and clarified separately by centrifugation and filtration prior to inactivation with β -propiolactone. The inactivated virus is concentrated and purified by zonal centrifugation. The surface antigens, HA and neuraminidase, are obtained from the influenza virus particle by further centrifugation in the presence of nonylphenol ethoxylate, a process which removes most of the internal proteins. The nonylphenol ethoxylate is removed from the surface antigen preparation.

Fluvirin is a homogenized, sterile, slightly opalescent suspension in a phosphate buffered saline. Fluvirin has been standardized according to USPHS requirements for the current influenza season and is formulated to contain 45 mcg HA per 0.5-mL dose in the recommended ratio of 15 mcg HA of each of the three selected viruses.

Each dose of Fluvirin may contain residual amounts of egg proteins (≤ 1 mcg ovalbumin), polymyxin (≤ 3.75 mcg), neomycin (≤ 2.5 mcg), β -propiolactone (not more than 0.5 mcg) and nonylphenol ethoxylate (not more than 0.015% weight/volume).

The 0.5-mL prefilled syringe presentation is formulated without preservative. However, thimerosal, a mercury derivative used during manufacturing, is removed by subsequent purification steps to a trace amount (≤ 1 mcg mercury per 0.5-mL dose). Also, the tip caps of the prefilled syringes may contain natural rubber latex.

The 5-mL multidose vial formulation contains thimerosal, a mercury derivative, added as a preservative. Each 0.5-mL dose from the multidose vial contains 25 mcg mercury.

Fluzone High-Dose: Fluzone High-Dose is an inactivated influenza vaccine prepared from influenza viruses propagated in embryonated chicken eggs.¹⁴ The virus-containing allantoic fluid is harvested and inactivated with formaldehyde. Influenza virus is concentrated and purified in a linear sucrose density gradient solution using a continuous flow centrifuge. The virus is then chemically disrupted using a non-ionic surfactant, octylphenol ethoxylate (Triton X-100), producing a "split virus." The split virus is further purified and then suspended in sodium phosphate-buffered isotonic sodium chloride solution. The Fluzone High-Dose process uses an additional concentration factor after the ultrafiltration step in order to obtain a higher HA antigen concentration.

Fluzone High-Dose is standardized according to USPHS requirements and is formulated to contain 180 mcg HA total per 0.5-mL dose, with influenza strains recommended for the current flu season.

Fluzone High-Dose suspension is clear and slightly opalescent and is distributed in a 0.5-mL, single-dose prefilled syringe. Neither antibiotics nor preservative are used in the manufacture of Fluzone High-Dose. The prefilled syringe presentation is not made with natural rubber latex.

5.3.2 Dosing, administration, and duration of therapy

The study vaccine is administered as a single 0.5-mL intramuscular injection in the deltoid region of the upper arm. Each dose will be obtained from the NIH pharmacy and administered by qualified personnel according to standard procedures. The study vaccine should be shaken vigorously before use (for the multi-dose vial, shake the vial each time before withdrawing a dose). It should be inspected visually for particulate matter and discoloration prior to administration, whenever solution and container permit. After agitation, the study vaccine should be a slightly opalescent suspension. Use a separate sterile syringe and needle for each injection. It is recommended that small syringes (0.5 mL or 1 mL) should be used to minimize any product loss.

5.3.3 Dose delays

Vaccination will be delayed if a subject has evidence of acute infection (or another condition at the discretion of the PI) on the day of vaccine administration.

5.4 Concomitant Medications and Procedures

All concomitant prescription and nonprescription (including over-the-counter) medications taken during study participation will be recorded. For this protocol, a prescription medication is defined as a medication that can be prescribed only by a properly authorized/licensed clinician.

5.5 Prohibited Medications and Procedures

Receipt of additional vaccines, blood transfusion, and surgery will not be permitted prior to day 100 unless discussed with and approved by the PI. The individual's study schedule may be adjusted or ended early for that year of participation.

6 Study Schedule

All study visits will take place at the NIH CC. Subjects will be recruited as described in section 4.1 and will then sign the informed consent document before undergoing any research procedures. The study schedule is described below and in Appendix A. The subject may optionally repeat the schedule outlined below in each subsequent influenza season until the end of the study.

6.1 Screening (day -30 to -7)

In the first year of participation, screening will include an in-person health/medication history and physical exam (including height and weight measurement for BMI) as well as the evaluations listed below. For optional participation in subsequent influenza seasons, screening will have the same evaluations but an electronic REDCap health history and medication questionnaire instead of an in-person history/physical, and subjects will be asked their height and weight to estimate BMI. For individuals who report a history of SARS-CoV-2 infection, we will also review COVID-19 symptoms and/or documentation of SARS-CoV-2 testing (from the NIH or outside since December 2019).

The following evaluations will be conducted at the screening visit:

- Urine or serum pregnancy test for women of childbearing potential.
- Blood draw for the following screening tests:
 - CBC with differential.
 - Lymphocyte phenotyping with TBNK.
 - Acute care, mineral, and hepatic panels.
 - Anti-CMV IgG and IgM antibody and anti-EBV antibody panel.
 - Anti-HIV 1/2 antibody, antibody to hepatitis B surface antigen, and anti-hepatitis C virus antibody.
 - SARS-CoV-2 serum antibody test for individuals who do not provide documentation of a positive FDA-approved antibody test result (since December 2019).
 - If an individual with a documented positive SARS-CoV-2 PCR test result is tested for antibodies at screening and the result is negative, antibody testing will be repeated (possibly with a different FDA-approved test). If the second antibody test is negative, the individual will only be eligible to enroll in the cohort with no history of SARS-CoV-2 infection.

If any of these evaluations have been conducted on another protocol at the NIH within the previous 30 days, then they will not be repeated, and those results will be used to determine eligibility on this study. The exception is the pregnancy test, which must be done at the NIH within the previous 2 days. Screening labs conducted under this protocol may be repeated at the discretion of the PI within 30 days.

If the results of any screening tests are consistent with a previously unknown health condition or other incidental findings, then the subject will be informed of the results. The results will also be provided to the subject's primary physician if requested. If the subject does not have a primary

physician, then the study team will assist in referring them to an appropriate medical care provider for evaluation.

To reduce the number of visits and venipunctures, the screening visit may be combined with baseline (below) so all samples can be collected in one day. If a subject is determined to not be eligible for this study, then their samples will be appropriately discarded. The subject may also return for the baseline visit at a later date.

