3.1 Description of the Study Design

This is a prospective, open-label, exploratory study to evaluate the baseline immune state and post-vaccination immune responses of healthy volunteers to the seasonal influenza vaccine. The study vaccine is approved and indicated by the US Food and Drug Administration (FDA) for active immunization for the prevention of influenza disease caused by influenza virus subtypes A and B. Blood samples will be collected at various timepoints before and up to 100 days after vaccination to explore short- and long-term immunological effects of immunization. Blood may also be collected at optional monthly study visits up until 1 year after vaccination. Subjects may optionally provide stool samples on days -7, 0, 28, and 100.

Subjects will remain on study and may optionally repeat study visits (including vaccination) annually through the 2023-24 influenza season, with final study follow-up up to 1 year after vaccination. Sampling individual subjects across several influenza seasons will allow us to monitor for multi-season responses.

Blood will be evaluated to characterize immune response parameters, primarily changes in antibody titers following vaccination. These evaluations will be used to assess expected response to the vaccination in order to identify baseline and early response correlates of vaccination responses (e.g., by searching among the many parameters we will measure, as listed in section 7.2). Other important immune response parameters include the frequency of peripheral monocytes and interferon transcriptomic signatures (past studies suggest both can be detected in the blood on day 1 following influenza vaccination), as well as the frequency of plasmablast and certain CD4⁺ T-cell subsets (detectable around day 7 in past studies with influenza vaccination). In this study, these parameters should be captured exactly on days 1 and 7, as the earlier CHI study of influenza vaccination demonstrated that measuring these on the specified days will minimize variability and maximize detection of biologically important signals.³ Additional research evaluations may include flow cytometry and transcriptome and genetic analyses.

In year 2 of this protocol, enrollment will be enriched according to history of SARS-CoV-2 infection. We will enroll up to 120 subjects by consecutive sampling in the following cohorts:

- Up to n=40 subjects with no history of SARS-CoV-2 infection, as determined by a negative antibody test at screening.

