- Up to n=40 subjects with confirmed symptomatic SARS-CoV-2 infection, as determined by a documented positive polymerase chain reaction (PCR) test, and a positive antibody test at screening.
- Up to n=40 subjects with confirmed SARS-CoV-2 antibodies at screening or from an FDA-approved test as documented by the subject but with no history of symptoms.

This design will allow comparison between cohorts to explore the long-term immunological effects of SARS-CoV-2 infection. Recruitment in year 2 will be targeted toward these groups, and enrollment for each cohort will be stopped when its sample size is achieved for the year.

Because the vaccine response to the seasonal influenza vaccine in AA people has only started to be explored,¹⁰ we will recruit up to 10 AA subjects (of the 40) for each group described above in order to evaluate the relationship between AA race and vaccine responses in each of the three cohorts above.

Because obesity is associated with decreased vaccine responsiveness,¹¹ we will exclude individuals with a body mass index (BMI) ≥ 30 .

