3.2.2 Secondary endpoints

- Change in antibody titer response to vaccination, as measured by microneutralization titers at day 0 and day 70 and its relationship with established baseline biomarkers (CD38⁺ CD20⁺ B cell frequencies and/or transcriptomic signatures) and post-vaccination biomarkers (plasmablast cell frequencies and/or transcriptomic signatures)
- Difference in antibody titer response to vaccination between subjects with a history of symptomatic or asymptomatic SARS-CoV-2 infection and those with no evidence of SARS-CoV-2 infection

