15.3 Description of the Analyses

The primary analysis will be to correlate multiple baseline biomarkers with the vaccine-induced outcome adjMFC using GEE to reflect clustering at the subject level due to multiple measurements over multiple years. Analyses will be stratified by year by including a separate term for each cohort year in the GEE models. Two-sided testing will be performed with an adjustment for multiplicity such as the Bonferroni to control the overall type I error rate at 0.05.

For the first secondary analysis, a similar analysis strategy will be used as in the primary analysis, but the relationship between the vaccine-induced outcome adjMFC and baseline biomarkers (specifically ID_96 [CD38⁺ CD20⁺ B cell frequencies and/or transcriptomic signatures]) and post-vaccination biomarkers (specifically ID_87 [plasmablast cell frequencies and/or transcriptomic signatures]) will be examined separately. Specifically, we will evaluate 1) whether the slope between adjMFC and ID96_0 (measured at day 0) is zero using GEE, as described for the primary analysis with no adjustment for multiplicity, and 2) whether the slope between adjMFC and ID_87, measured at day 7/day 0) is zero using GEE, as described for the primary analysis with no adjustment for multiplicity. Both analyses are designed to replicate findings from 09-H-0239.³

Analysis of the secondary endpoint on SARS-CoV-2 will involve comparing the results of the above analyses by cohort: 1) those subjects with prior symptomatic SARS-CoV-2 infection, 2) those subjects with prior asymptomatic SARS-CoV-2 infection, and 3) those subjects without a history of SARS-CoV-2 infection.

The exploratory analyses will involve both unsupervised and supervised analyses using the framework developed in 09-H-0239. In addition to that framework, under this protocol we will be able to characterize immune responses and biomarker relationships over multiple seasons in the same individual. The first general aim is to perform unsupervised analysis of the immune states of the baseline along the measured phenotypic dimensions, including PBMC/cell subset

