Appendix A. Schedule of Procedures/Evaluations

Evaluation	Study Day (window) ^a									
	Screening	Baseline	Vaccination	Follow-up						Optional Follow-up
	(-30 to -7)	-7 (± 2)	0	1 (± 0)	7 (± 0)	14 (± 1)	28 (± 2)	70 (± 2)	100 (± 7) ^b	Monthly ^c
Informed consent	X									
Clinical Procedures and Evaluations										
History, physical exam with height and weight (for BMI), and vital signs	X									
Electronic history/medication questionnaire		X ^d	X	X	X	X	X	X	X	X
Electronic AE questionnaire				X	X					
Vaccination			X ^e							
Stool collection (optional) ^f		X	X				X		X	
Clinical Laboratory Evaluations										
Blood Volume (mL)										
Urine/serum pregnancy test (women of childbearing potential)	4 ^g	4 ^d								
SARS-CoV-2 antibody	X									
CBC with differential	3 ^h	3 ^d	3	3	3	3	3	3	3	3
TBNK lymphocyte phenotyping	3 ^h	3 ^d	3	3	3	3	3	3	3	3
Acute care, mineral, and hepatic panels	4 ^h									
Anti-CMV IgG, IgM antibody and anti-EBV antibody panel	4 ^h									
Anti-HIV 1/2 antibody, antibody to hepatitis B surface antigen, and anti-hepatitis C virus antibody	8 ^h									
Research Laboratory Evaluations										
Blood Volume (mL)										
Serum isolation		4	4	4	4	4	4	4	4	4
PBMC isolation		60	90	40	40	40	40	40	40	40
Whole-blood RNA isolation		6	6	6	6	6	6	6	6	6
Daily Blood Volume	26	80	106	56	56	56	56	56	56	56
Cumulative Blood Volume	26	106	212	268	324	380	436	492	548	
Abbreviations: AE, adverse event; BMI, body mass index; CBC, complete blood count; CMV, cytomegalovirus; EBV, Epstein-Barr virus; HIV, human immunodeficiency virus; Ig, immunoglobulin; PBMC, peripheral blood mononuclear cell; RNA, ribonucleic acid; TBNK = T, B, and natural killer cells.										
^a After the first year of participation, subjects may repeat the study schedule annually through the 2023-24 influenza season. Screening will be repeated each year except the informed consent process and the history/physical exam/vital signs, which will be replaced with the electronic history/medication questionnaire. Subjects who are ineligible for that year will remain on study and may return to participate the following year if they are eligible.										
^b Subjects withdrawn before day 100 will be encouraged to have an early termination visit to complete procedures for the day 100 visit.										
^c Once per calendar month starting the calendar month after the day 100 visit, as requested up until 1 year following vaccination (up to 8 optional visits per year).										

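### Section 6.1 routes people with a documented positive SARS-CoV-2 PCR into the no-history reference cohort, and the antibody-test rule for the symptomatic cohort is inconsistent

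*Combined protocol and SAP*

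**What the plan says.** Section 3.1 sets up three year-2 cohorts of up to 40 subjects each.

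- **No history:** "no history of SARS-CoV-2 infection, as determined by a negative antibody test at screening".
- **Symptomatic:** confirmed infection, "as determined by a documented positive polymerase chain reaction (PCR) test, and a positive antibody test at screening".
- **Asymptomatic:** "confirmed SARS-CoV-2 antibodies at screening or from an FDA-approved test as documented by the subject but with no history of symptoms".

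Section 6.1 governs who is tested. It lists a "SARS-CoV-2 serum antibody test for individuals who do not provide documentation of a positive FDA-approved antibody test result (since December 2019". A person with a documented positive PCR who is tested and found antibody-negative is retested, possibly with a different assay. Then: "If the second antibody test is negative, the individual will only be eligible to enroll in the cohort with no history of SARS-CoV-2 infection".

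The screening column of Appendix A marks the "SARS-CoV-2 antibody" row with no footnote or exception.

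The secondary endpoint in Section 3.2.2 sets subjects with symptomatic or asymptomatic infection against "those with no evidence of SARS-CoV-2 infection". Section 15.3 describes the third analysis group as "those subjects without a history of SARS-CoV-2 infection".

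**The concern.** There are two separate problems.

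The more important one is the routing rule. The reference group of a named secondary comparison is meant to contain people with no sign of past infection, yet Section 6.1 makes it the only cohort open to certain people who hold a positive PCR result. Section 1.1.2 motivates the comparison by suggesting that infection may affect immunological memory and later vaccine responses. Previously infected people without detectable antibodies are directly relevant to that question, and the rule puts them on the uninfected side.

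The second problem is confined to the symptomatic cohort. Section 3.1 requires an antibody test at screening, whereas Section 6.1 omits it for anyone who brings an earlier positive report. Two people with the same infection and the same current serostatus can then be handled differently because one kept a document.

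**Working it through.** No figure in the plan can be reproduced here. Section 15.2 powers only the slope between a biomarker and adjMFC; the cohort comparison has no power calculation. The check is a trace of the rules.

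**Routing rule against endpoint**

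1. Take a person with a documented positive PCR and no earlier positive antibody report. Section 6.1 requires an antibody test.
2. The result is negative, the test is repeated, and it is negative again.
3. Section 6.1 leaves only the no-history cohort. This is consistent with Section 3.1, which defines that cohort by serology alone.
4. Section 3.2.2 requires no evidence of infection and Section 15.3 requires no history of it. A documented positive PCR fails both descriptions. Section 3.1 itself uses such a PCR as one of the two proofs of infection for the symptomatic cohort.

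**Testing rule, symptomatic cohort**

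Take a symptomatic, PCR-positive person whose antibodies are no longer detectable.

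- *With an earlier positive antibody report:* Section 6.1 requires no test. If the report is accepted, the person enters the symptomatic cohort. On a strict reading of Section 3.1 the person has no positive test at screening and fits no infected cohort.
- *Without the report:* the person is tested, is negative twice, and may enter only the no-history cohort.

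The outcome turns on the antibody report; the PCR document only triggers the repeat test. Reading Section 3.1's screening requirement to include documents reviewed at screening is weak, because the asymptomatic definition names the test and the document as two distinct routes.

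**Does testing everyone cure the first problem?** No. The waiver keeps people with an old report away from the no-history cohort. Testing all of them under the present routing rule could send more previously infected people into the reference group.

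**Effect on the comparison**

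Let D be the true mean difference between infected and uninfected subjects, and w the share of the reference group that was in fact infected. If those people respond as the infected cohorts do, the expected contrast is D × (1 − w). In a full cohort of 40, each such person contributes 1/40 = 2.5% to w. The documents give neither a rate of antibody loss nor an expected number of such volunteers, so w cannot be estimated.

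The direction rests on that assumption. If people who lose antibodies are also weaker responders to influenza vaccine, moving them changes the mean of both groups, and attenuation is likely but not certain.

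**The case against.** The best defence is that two negative antibody tests, possibly on different assays, cast doubt on the PCR result, and that Section 3.1 deliberately defines no history by serology. That could justify leaving these people out or running a sensitivity analysis. It does not justify analysing them as having no evidence of infection while they hold a positive PCR.

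Several limits stand.

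- A reader might infer that both infected cohorts are caught in a contradiction over testing. They are not: for asymptomatic subjects, Sections 3.1 and 6.1 both accept a documented result, so that route is a consistent design choice.
- A reader might want to attach a percentage dilution or a sample-size inflation. The documents supply no basis for one, and this comparison has no power-based sample size to inflate. Section 15.2 calls the study hypothesis-generating.
- A reader might conclude that serostatus at vaccination can never be known. Section 7.2 lists a SARS-CoV-2 antibody assay among the additional evaluations on pre- and post-vaccination samples. The wording is permissive, so testing is possible but not assured.
- The opposite-cohort outcome needs someone whose screening test would be negative, and it needs the site to accept a report where Section 3.1 asks for a test.

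**Conclusion.** The plan is wrong as written on the routing rule. Followed literally, it places people with documented infection in a reference group that the endpoint and the analysis section describe as free of it. The probable effect is attenuation of the SARS-CoV-2 cohort comparison. Its size is unknown, and its direction assumes that antibody-negative, previously infected people respond broadly like the other infected subjects.

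The testing conflict between Sections 3.1 and 6.1 and Appendix A is also real, but it concerns only the symptomatic cohort and matters only for people whose antibodies have waned. It is not the source of the reference-group contamination.

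The damage is to a secondary comparison. Nothing here shows that the primary biomarker analysis is affected.

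**What to change.** 1. Reconcile Sections 3.1, 3.2.2, 6.1 and 15.3 and Appendix A so that nobody with a documented positive PCR or antibody result is classed or analysed as no history.
2. State what happens to PCR-positive, antibody-negative people: either they are left out of the three-cohort comparison, or they form a separate previously infected, seronegative group. Without this they fit no cohort once the first change is made.
3. Apply one antibody-testing rule to the symptomatic cohort and make Section 3.1, Section 6.1 and Appendix A agree on it.
4. Commit to measuring baseline serostatus on the serum already scheduled at day -7 or day 0, with the assay already listed in Section 7.2. Use it as a covariate or in a sensitivity analysis. Cohort and serostatus will overlap heavily, so a sensitivity analysis among the previously infected is likely to be the more informative use.

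The cost is a few sentences across these sections, a modest number of assays on serum already collected, and perhaps a few subjects lost from the comparison. The change cannot identify infected people who have neither a document nor detectable antibodies; that residual misclassification should be acknowledged when the comparison is reported.
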